**2. Have you experienced any vomiting in the last 24 hours?**

- No
- Yes → Please record on the Retching and/or Vomiting page (page 12).

**3. Has there been a change in your appetite?**

- No change in appetite
- Nausea – lost appetite but able to eat as usual
- Nausea – lost appetite but able to eat a reduced amount
- Nausea – lost appetite and unable to eat

**4. Did you take any medications because of severe nausea?**

- No
- Yes → Please record on the Rescue Medication page (page 14).

CAN-PRO-NEPA-001	PATIENT DIARY	
 
  	 	 	-	 	 	 	-	 	
 
 Site Number		Patient Number		Cycle #	
 
				-				-		Site Number				Patient Number				Cycle #
					-				-											
Site Number				Patient Number				Cycle #												
	DAILY EVALUATION																			

DAY 2 EVALUATION: >24 - 48 HOURS AFTER START OF CHEMOTHERAPY																													
Please complete the page on: (for study personnel only)	
 
  	 	/	 	 	 	/	 	 	 	 	:	 	 	
 
 dd		mmm		yyyy		hh	mm	
 
			/				/					:			dd			mmm				yyyy					hh	mm
		/				/					:																		
dd			mmm				yyyy					hh	mm																

Please remember to record any experience of retching (unproductive vomiting) and/or vomiting on pages 12 to 13 and the medication(s) you took for the treatment of nausea and/or vomiting on pages 14 to 15.

Please evaluate your severity of nausea for the >24 to 48-hour interval after the start of chemotherapy.

Example: Start of chemotherapy – 01June2018 @ 08:00  
 Period of evaluation = 02June2018 @ 08:00 to 03June2018 @ 07:59

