### GENERAL INSTRUCTIONS

- Please bring back the diary at each study visit.
- Please make sure that all writing is clear and readable.
- If you make a mistake, cross it out and make your change readable. Please do not use liquid paper or white out to make your changes.
- Please record the dates and times in the following format:

Date: dd/mmm/yyyy (i.e., 12/Mar/2018)

Hour: hh:mm (24-hour clock) (i.e., 18:45)

- Please complete all questions. Do not leave blank spaces.

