**RETCHING (UNPRODUCTIVE VOMITING) AND/OR VOMITING**

- If you experienced a retching (unproductive vomiting) or vomiting episode during the 120 hours (5 days) after the start of chemotherapy, please check "Yes" and record the date, onset time and end time of each episode of retching and vomiting.
- Please record the date and onset/end time in the most precise manner.
- If you did not experience any retching or vomiting episodes, please remember to check "No" before returning the diary to the Investigator at your next visit.

	Did you experience any episodes of retching and/or vomiting during the 120 hours (5 days) after the start of chemotherapy?	Yes 
		No 

Retching	Vomiting	Date	Onset Time 00:00 – 23:59	End Time 00:00 – 23:59
		01 / Jun / 2018 <small>dd mmm yyyy</small>	08 : 35 <small>hh mm</small>	08 : 55 <small>hh mm</small>
The first row is pre-filled as an example				
		 /  /  <small>dd mmm yyyy</small>	 :  <small>hh mm</small>	 :  <small>hh mm</small>
		 /  /  <small>dd mmm yyyy</small>	 :  <small>hh mm</small>	 :  <small>hh mm</small>
		 /  /  <small>dd mmm yyyy</small>	 :  <small>hh mm</small>	 :  <small>hh mm</small>
		 /  /  <small>dd mmm yyyy</small>	 :  <small>hh mm</small>	 :  <small>hh mm</small>
		 /  /  <small>dd mmm yyyy</small>	 :  <small>hh mm</small>	 :  <small>hh mm</small>

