**RESCUE MEDICATION**

	Did you take medication for the treatment of nausea and/or vomiting during the 120 hours (5 days) after the start of chemotherapy?	Yes  No 
--	-------------------------------------------------------------------------------------------------------------------------------------------	-------------------------------------------------------------

- *If you checked "Yes", please record every medication you take for the treatment of nausea and/or vomiting during the 120 hours (5 days) after the start of chemotherapy.*
- *Please record the date and time taken in the most precise manner.*
- *For each medication taken, please record the dose, route and quantity.*

Medication <small>Please list every administration of medication separately</small>	Dose <small>(e.g., 10 mg)</small>	Route <small>(e.g., oral, rectal, topical, intravenous)</small>	Quantity <small>(e.g., 1 tablet)</small>	Date and Time of Intake of Medication <small>Please record the date and time of each medication taken.</small> <small>(00:00 – 23:59)</small>	
Prochlorperazine	10 mg	Oral	1 tablet	01 / Jun / 2018	10 : 25
The first row is pre-filled as an example.				 /  / 	 : 
				 /  / 	 : 
				 /  / 	 : 
				 /  / 	 : 
				 /  / 	 : 

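### Diary items 4 and 2 ask about less than the logs they point to: align the wording on all five day pages and set one either-source rule in the SAP

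*Combined protocol and SAP*

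**What the plan says.** Section 2.2 defines CR as no emetic episode and no rescue medication over 0-120 hours, and lists rescue use by day. Neither is limited by the reason for the dose or by the severity of nausea. Section 2.2 derives these, and time to failure, from the patient diary as a whole. It does not say whether the daily item or the log is the source. Section 3.5 adds CR in the acute, delayed and overall phases for all cycles.

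The diary (Appendix 2) collects the same facts in two places.

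- **Rescue.** Item 4 on each day page asks "Did you take any medications because of severe nausea" and sends a patient who answers Yes to the Rescue Medication Log. That log has its own 120-hour Yes/No question and then says "please record every medication you take for the treatment of nausea and/or vomiting", with "Please record the date and time of each medication taken".
- **Emesis.** Item 2 on each day page asks "Have you experienced any vomiting in the last 24 hours" and sends a patient who answers Yes to the Retching and/or Vomiting Log. That log opens "If you experienced a retching (unproductive vomiting) or vomiting episode during the 120 hours (5 days) after the start of chemotherapy" and asks for onset and end times.

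Every day page also carries a reminder in the logs' wider terms, beginning "Please remember to record any experience of retching (unproductive vomiting) and/or vomiting on pages 12 to 13" and going on to medication for nausea or vomiting. The General Instructions add "Please complete all questions. Do not leave blank spaces".

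Section 7.3 excludes implausible or ambiguous data, and leaves the analysis details to an SAP to be prepared before database lock.

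**The concern.** Item 4 is the only rescue question put to the patient each day, and it leaves out doses taken for vomiting or for nausea that is not severe. Item 2 leaves out retching without vomiting. Both items are narrower than the log they lead to, and item 4 is also narrower than the endpoints.

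Two things could follow. A patient who takes the day page as the guide to what counts may not open the log. And a No on the day page beside a log entry, though perfectly consistent, may look like a conflict to whoever cleans the data. Either way the error runs in one direction: CR goes up and recorded rescue use goes down.

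**Working it through.** The plan states no figure for this point, so the check is a comparison of texts followed by an illustration of size.

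**1. What a fully truthful patient would record**

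| Event | Day page | Log | Endpoint |
|---|---|---|---|
| Medication for severe nausea | Item 4 Yes | Entry | Rescue use, not CR |
| Medication for mild or moderate nausea | Item 4 No | Entry | Rescue use, not CR |
| Medication for vomiting, without severe nausea | Item 4 No | Entry | Rescue use, not CR |
| Vomiting | Item 2 Yes | Entry | Not CR |
| Retching without vomiting | Item 2 No | Entry | Not stated |

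Rows 2, 3 and 5 are the mismatch. The wording is the same on Days 1 to 5. The last cell of row 5 is open because no section says whether retching alone is an emetic episode.

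**2. When a loss would arise**

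With complete logs used as the source, rows 2 and 3 are counted correctly, and row 5 can be counted once its status is settled; the loss is 0. A loss needs one of three things: an unfilled log, item 4 used as the source for rescue, or discordant entries dropped as ambiguous. The documents commit to none of these and exclude none of them.

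**3. Illustration of size for item 4**

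A missed rescue dose changes CR only in a patient without emesis. Inputs from Section 1.4, Study 2, NEPA arm, overall period: no vomiting 79.8%, CR 74.3%.

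- Rescue-only failures: 79.8 - 74.3 = 5.5% of patients. The palonosetron arm gives the same: 72.1 - 66.6 = 5.5%.
- At 200 patients: 0.055 x 200 = 11 per cycle.
- If 10% of these went unrecorded, CR would rise by 0.10 x 5.5 = 0.55 point; if 25%, by 0.25 x 5.5 = 1.4 points.
- If all 11 were excluded as ambiguous, CR would read 74.3 / (100 - 5.5) = 78.6%, up 4.3 points.
- For scale, the 95% half-width of a CR of 74.3% at n = 200 is 1.96 x sqrt(0.743 x 0.257 / 200) = 6.1 points.

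On the same rates, patients using any rescue lie between 5.5% (rescue-only failures) and 100 - 74.3 = 25.7% (all CR failures), or 11 to 51 of 200. Some unknown part of them would be missed if item 4 were the source for daily rescue use.

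These figures assume that the cited rates apply here and share one denominator. The 10% and 25% are chosen for illustration. The documents give no figure for retching alone, or for how many doses are taken for vomiting or non-severe nausea.

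**The case against.** The strongest reply is that the diary already deals with this. The daily items are cues and do not control access to the logs. The reminder on every day page is unconditional and uses the full scope. Each log asks its own Yes/No question, and patients without emesis are told "If you did not experience any retching or vomiting episodes, please remember to check" No. Staff review the diary with the patient (Appendix 2, introduction). Concomitant medication is assessed at Visits 2 to 6 (Sections 6.2 to 6.6) and recorded in the CRF (Section 5.2). Section 12.4 provides a study-specific validation plan and requires the physician to supply background information on request, and Section 13.1 adds monitoring against source. The rescue log lists each administration with date and time, so daily rescue use can be derived from it. Naming the source field is ordinary SAP content, and the SAP is still to come.

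Most of this stands, and it is why the likely loss is small. It does not remove the mismatch. These measures protect the completeness and accuracy of the record, but they do not say which source governs or how a daily No beside a log entry is to be read.

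A reader might also count the missing time window in item 4 as a defect. It is not: the header of each day page gives the interval in hours.

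**Conclusion.** The mismatch is real on all five day pages and worth correcting, as a cheap improvement and not as a threat to the study. Its floor is zero and its expected size cannot be estimated from the documents. It bears only on secondary, descriptive endpoints: CR, rescue use and time to failure. The primary endpoint, the cycle 1 FLIE total score (Section 3.4), is untouched.

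Three stronger readings are not supported.

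- *That 5.5 points is a ceiling.* It comes from one trial in chemotherapy-naive patients on AC-based treatment. This study admits any highly emetogenic regimen (Section 4.1), including cisplatin (Appendix 5), and does not require chemotherapy-naive patients. Rescue-only failure here could be higher or lower.
- *That CR will be inflated by several points.* If CR were scored from the daily items alone, and an assumed 5% to 30% of failures were invisible to them, CR would rise by 0.257 x 5% = 1.3 to 0.257 x 30% = 7.7 points. No section proposes that scoring, and the share is a guess.
- *That Section 7.3 will remove discordant diaries.* A truthful No beside a log entry need not be classed as ambiguous, and the content of the validation plan is not given, so such entries may well be queried first. The documents only leave the possibility open.

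**What to change.** **Diary, all five day pages.** Reword item 4 to ask whether any medication was taken to treat nausea or vomiting in the last 24 hours. Reword item 2 to ask about retching and vomiting in the last 24 hours, with separate boxes for each, as in the log. The time phrase in item 4 is for consistency with items 1 and 2.

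**SAP, one rule in four parts.**

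1. A day or cycle has rescue use or an emetic episode if either the log or the daily item shows it. Apply this to both CR and daily rescue use, so that a patient cannot fail CR through rescue and yet show no rescue on any day.
2. Take event times from the log. For time to failure, treat a daily Yes with no log row as an event at an unknown time within that 24-hour day.
3. State whether retching alone is an emetic episode. Without this the rule cannot classify a retching-only cycle.
4. State that a daily No beside a log entry is an event and is not excluded as ambiguous under Section 7.3.

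**Cost.** Two items on five pages, REB approval of the revised diary (Section 11.1) at up to 20 sites (Section 3.2), and possibly a slightly lower observed CR. If diaries are already in use, apply the SAP rule alone.

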**1. NAUSEA**

How much nausea did you experience on average during the last 24 hours?

Please mark on the following scale with a straight vertical line:

No nausea
	
Always severe nausea
	
Nausea (for study personnel only)
 
 
  	 	 	
 
 mm	
 
				mm		
mm								
0 mm	100 mm							

**2. Have you experienced any vomiting in the last 24 hours?**

- No
- Yes → Please record on the Retching and/or Vomiting page (page 12).

**3. Has there been a change in your appetite?**

- No change in appetite
- Nausea – lost appetite but able to eat as usual
- Nausea – lost appetite but able to eat a reduced amount
- Nausea – lost appetite and unable to eat

**4. Did you take any medications because of severe nausea?**

- No
- Yes → Please record on the Rescue Medication page (page 14).

CAN-PRO-NEPA-001	PATIENT DIARY DAILY EVALUATION	
 
 									
 
 Site Number	Patient Number	Cycle #	
 
										Site Number			Patient Number			Cycle #		
Site Number			Patient Number			Cycle #														

DAY 3 EVALUATION: >48 - 72 HOURS AFTER START OF CHEMOTHERAPY																				
Please complete the page on: <small>(for study personnel only)</small>	
 
 		
 
 <small>dd</small>	<small>mm</small>	
 
			<small>dd</small>	<small>mm</small>	
 
 				
 
 <small>yyyy</small>	<small>hh</small>	<small>mm</small>	<small>mm</small>	
 
					<small>yyyy</small>	<small>hh</small>	<small>mm</small>	<small>mm</small>	
 
 		
 
 <small>hh</small>	<small>mm</small>	
 
			<small>hh</small>	<small>mm</small>	
<small>dd</small>	<small>mm</small>																			
<small>yyyy</small>	<small>hh</small>	<small>mm</small>	<small>mm</small>																	
<small>hh</small>	<small>mm</small>																			

*Please remember to record any experience of retching (unproductive vomiting) and/or vomiting on pages 12 to 13 and the medication(s) you took for the treatment of nausea and/or vomiting on pages 14 to 15.*

*Please evaluate your severity of nausea for the >48 to 72-hour interval after the start of chemotherapy.*

*Example: Start of chemotherapy – 01June2018 @ 08:00  
Period of evaluation = 03June2018 @ 08:00 to 04June2018 @ 07:59*

**1. NAUSEA**

How much nausea did you experience on average during the last 24 hours?

*Please mark on the following scale with a straight vertical line:*

 No nausea 0 mm	 Always severe nausea 100 mm	Nausea (for study personnel only) 
 
 			
 
 <small>mm</small>	
 
				<small>mm</small>		
<small>mm</small>								

**2. Have you experienced any vomiting in the last 24 hours?**

- No
- Yes → Please record on the Retching and/or Vomiting page (page 12).

**3. Has there been a change in your appetite?**

- No change in appetite
- Nausea – lost appetite but able to eat as usual
- Nausea – lost appetite but able to eat a reduced amount
- Nausea – lost appetite and unable to eat

**4. Did you take any medications because of severe nausea?**

- No
- Yes → Please record on the Rescue Medication page (page 14).

CAN-PRO-NEPA-001	PATIENT DIARY DAILY EVALUATION	[ ] [ ] [ ] - [ ] [ ] [ ] - [ ]
		Site Number      Patient Number      Cycle #

DAY 4 EVALUATION: >72 - 96 HOURS AFTER START OF CHEMOTHERAPY			
Please complete the page on: (for study personnel only)	[ ] [ ] / [ ] [ ] [ ] / [ ] [ ] [ ] [ ]	[ ] [ ] : [ ] [ ]	
	dd / mmm / yyyy	hh : mm	

Please remember to record any experience of retching (unproductive vomiting) and/or vomiting on pages 12 to 13 and the medication(s) you took for the treatment of nausea and/or vomiting on pages 14 to 15.

Please evaluate your severity of nausea for the >72 to 96-hour interval after the start of chemotherapy.

Example: Start of chemotherapy – 01June2018 @ 08:00  
Period of evaluation = 04June2018 @ 08:00 to 05June2018 @ 07:59

**1. NAUSEA**

How much nausea did you experience on average during the last 24 hours?

Please mark on the following scale with a straight vertical line:

No nausea
	
Always severe nausea
	
Nausea (for study personnel only)
 
[ ] [ ] [ ] mm

0 mm	100 mm	

**2. Have you experienced any vomiting in the last 24 hours?**

- No
- Yes → Please record on the Retching and/or Vomiting page (page 12).

**3. Has there been a change in your appetite?**

- No change in appetite
- Nausea – lost appetite but able to eat as usual
- Nausea – lost appetite but able to eat a reduced amount
- Nausea – lost appetite and unable to eat

**4. Did you take any medications because of severe nausea?**

- No
- Yes → Please record on the Rescue Medication page (page 14).

CAN-PRO-NEPA-001	PATIENT DIARY DAILY EVALUATION	
 
  	 	 	 	-	 	 	 	 	-	 	 	
 
 Site Number		Patient Number		Cycle #	
 
					-					-			Site Number					Patient Number					Cycle #	
				-					-																	
Site Number					Patient Number					Cycle #																

DAY 5 EVALUATION: >96 - 120 HOURS AFTER START OF CHEMOTHERAPY																																				
Please complete the page on: (for study personnel only)	
 
  	 	/	 	 	 	 	/	 	 	 	 	
 
 dd		mmm		yyyy	
 
			/					/					dd			mmm					yyyy				
 
  	 	:	 	 	
 
 hh		mm	
 
			:			hh			mm	
		/					/																													
dd			mmm					yyyy																												
		:																																		
hh			mm																																	

Please remember to record any experience of retching (unproductive vomiting) and/or vomiting on pages 12 to 13 and the medication(s) you took for the treatment of nausea and/or vomiting on pages 14 to 15.

Please evaluate your severity of nausea for the >96 to 120-hour interval after the start of chemotherapy.

Example: Start of chemotherapy – 01June2018 @ 08:00

Period of evaluation = 05June2018 @ 08:00 to 06June2018 @ 07:59

### 1. NAUSEA

How much nausea did you experience on average during the last 24 hours?

Please mark on the following scale with a straight vertical line:

 No nausea 0 mm	 Always severe nausea 100 mm	Nausea (for study personnel only) 
 
  	 	 	 	
 
 mm	
 
					mm			
mm										

### 2. Have you experienced any vomiting in the last 24 hours?

- No  
 Yes → Please record on the Retching and/or Vomiting page (page 12).

### 3. Has there been a change in your appetite?

- No change in appetite  
 Nausea – lost appetite but able to eat as usual  
 Nausea – lost appetite but able to eat a reduced amount  
 Nausea – lost appetite and unable to eat

### 4. Did you take any medications because of severe nausea?

- No  
 Yes → Please record on the Rescue Medication page (page 14).

At the end of Day 5 evaluation, please complete the following questionnaires: *Functional Living Index – Emesis* and the *Work Productivity and Activity Impairment Questionnaire: Nausea & Vomiting*.

CAN-PRO-NEPA-001	PATIENT DIARY Retching and/or Vomiting Log	
 
 							
 
 Site Number	Patient Number	Cycle #	
 
										Site Number			Patient Number		Cycle #	
Site Number			Patient Number		Cycle #													

**RETCHING (UNPRODUCTIVE VOMITING) AND/OR VOMITING**

- If you experienced a retching (unproductive vomiting) or vomiting episode during the 120 hours (5 days) after the start of chemotherapy, please check "Yes" and record the date, onset time and end time of each episode of retching and vomiting.
- Please record the date and onset/end time in the most precise manner.
- If you did not experience any retching or vomiting episodes, please remember to check "No" before returning the diary to the Investigator at your next visit.

	Did you experience any episodes of retching and/or vomiting during the 120 hours (5 days) after the start of chemotherapy?	Yes 
		No 

Retching	Vomiting	Date	Onset Time 00:00 – 23:59	End Time 00:00 – 23:59
		01 / Jun / 2018 <small>dd mmm yyyy</small>	08 : 35 <small>hh mm</small>	08 : 55 <small>hh mm</small>
The first row is pre-filled as an example				
		 /  /  <small>dd mmm yyyy</small>	 :  <small>hh mm</small>	 :  <small>hh mm</small>
		 /  /  <small>dd mmm yyyy</small>	 :  <small>hh mm</small>	 :  <small>hh mm</small>
		 /  /  <small>dd mmm yyyy</small>	 :  <small>hh mm</small>	 :  <small>hh mm</small>
		 /  /  <small>dd mmm yyyy</small>	 :  <small>hh mm</small>	 :  <small>hh mm</small>
		 /  /  <small>dd mmm yyyy</small>	 :  <small>hh mm</small>	 :  <small>hh mm</small>
		 /  /  <small>dd mmm yyyy</small>	 :  <small>hh mm</small>	 :  <small>hh mm</small>
		 /  /  <small>dd mmm yyyy</small>	 :  <small>hh mm</small>	 :  <small>hh mm</small>

CAN-PRO-NEPA-001	PATIENT DIARY Rescue Medication Log	
 
 			Site Number	-					Patient Number	-		Cycle #	
 
				Site Number	-					Patient Number	-		Cycle #
			Site Number	-					Patient Number	-		Cycle #			

**RESCUE MEDICATION**

	Did you take medication for the treatment of nausea and/or vomiting during the 120 hours (5 days) after the start of chemotherapy?	Yes  No 
--	-------------------------------------------------------------------------------------------------------------------------------------------	-------------------------------------------------------------

- *If you checked "Yes", please record every medication you take for the treatment of nausea and/or vomiting during the 120 hours (5 days) after the start of chemotherapy.*
- *Please record the date and time taken in the most precise manner.*
- *For each medication taken, please record the dose, route and quantity.*

Medication <small>Please list every administration of medication separately</small>	Dose <small>(e.g., 10 mg)</small>	Route <small>(e.g., oral, rectal, topical, intravenous)</small>	Quantity <small>(e.g., 1 tablet)</small>	Date and Time of Intake of Medication <small>Please record the date and time of each medication taken.</small> <small>(00:00 – 23:59)</small>	
Prochlorperazine	10 mg	Oral	1 tablet	01 / Jun / 2018	10 : 25
The first row is pre-filled as an example.				 /  / 	 : 
				 /  / 	 : 
				 /  / 	 : 
				 /  / 	 : 
				 /  / 	 : 

CAN-PRO-NEPA-001	PATIENT DIARY EMERGENCY DEPARTMENT & HOSPITALIZATION	
 
 			-				-		
 
 Site Number		Patient Number		Cycle #	
 
				-				-		Site Number				Patient Number				Cycle #
			-				-													
Site Number				Patient Number				Cycle #												

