## 2.2 Secondary Outcomes

The response to Akynzeo® and the necessity for use of a rescue medication will be recorded to evaluate effectiveness. The medicinal products used as rescue medication will also be recorded. The following parameters will be calculated from information recorded in the patient diary:

- Complete Response (CR): no emetic episode and no use of rescue medication in the overall period (0-120h/Day 1-5)
- Severity of nausea (daily from Day 1 to Day 5) using a VAS scale (Visual Analogue Scale)
- Time to failure (time to first emetic episode or time to rescue)
- Use of rescue medication (daily from Day 1 to Day 5)

The collection of safety data and adverse events AEs in connection with administration of Akynzeo® will be performed.

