### 3.5 Secondary Endpoints

The secondary endpoints are:

- FLIE total score cycles 2-4
- FLIE Nausea domain total score all cycles
- FLIE Vomiting domain total score all cycles
- Complete response-no emesis, no rescue medication during the acute, delayed and overall phase all cycles
- No significant nausea during the acute, delayed and overall phase for all cycles
- Time to failure defined as time to first emetic episode or time to rescue medication use for all cycles
- Use of rescue medication all cycles
- To descriptively assess the patient diary at screening and over time

The response to Akynzeo® and the necessity for use of a rescue medication will be recorded to evaluate effectiveness. Any medicinal products used as rescue medication will be recorded in the patient diary.

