### 5.2 Concomitant Medication(s)

Other treatment considered necessary for the subject's welfare may be given at the discretion of the patients treating physician. All such therapy must be recorded in the Case Report Form.

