**EMERGENCY DEPARTMENT VISITS OR OVERNIGHT HOSPITALIZATION**

1. Did you visit an Emergency Department during the 120 hours (5 days) after the start of chemotherapy?  
 No    Yes → If you visited the Emergency Department, please check the applicable box(es) or provide the reason, and record the date, onset time and end time of each visit.

Nausea	Vomiting	Other Reason	Date	Onset Time 00:00 – 23:59	End Time 00:00 – 23:59																								
			
 
 										
 
 dd	mmm	yyyy	hh	mm	hh	mm	
 
											dd	mmm	yyyy	hh	mm	hh	mm	
 
 				
 
 hh	mm	hh	mm	
 
					hh	mm	hh	mm
dd	mmm	yyyy	hh	mm	hh	mm																							
hh	mm	hh	mm																										

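### Rescue use is derived from the patient diary alone, so an antiemetic given by ED or hospital staff for nausea and not logged by the patient leaves that patient a complete responder

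*Combined protocol and SAP*

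**What the plan says.** CR requires freedom from emesis and from rescue drugs over 0-120 h (Sections 2.2 and 6.7). Section 2.2 names one source for CR, rescue use and time to failure: "The following parameters will be calculated from information recorded in the patient diary". Section 3.5 agrees: "Any medicinal products used as rescue medication will be recorded in the patient diary".

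The rescue log in Appendix 2 opens with a Yes/No question on whether the patient took anything to treat nausea or vomiting in the 120 h. After a Yes it continues: "please record every medication you take for the treatment of nausea and/or vomiting". It also instructs "Please list every administration of medication separately", and its route column gives as examples "e.g., oral, rectal, topical, intravenous".

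Two other records may hold relevant information:

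- **The ED and overnight-hospitalization page of the same diary.** It says "If you visited the Emergency Department, please check the applicable box(es) or provide the reason", with boxes for nausea and vomiting and space for the date and times. It has no field for treatment given. Its data serve an exploratory endpoint (Section 3.6), tabulated in the Safety population (Section 7.3).
- **The concomitant-medication CRF.** Of other treatment given at the physician's discretion, Section 5.2 says "All such therapy must be recorded in the Case Report Form". Table 1 schedules a concomitant-medication assessment at Visits 2 to 6.

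The protocol gives neither record a role in deriving CR, rescue use or time to failure.

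**The concern.** A patient who goes to an ED or ward with bad nausea may be given an antiemetic by staff. A log worded around what the patient took, with a self-administered oral tablet as its worked example, may not prompt that patient to enter it. If there was no retching or vomiting and the drug is not logged, the diary shows neither component of failure and the patient is a complete responder. Yet the same booklet may show an ED visit for nausea, and the CRF may show the drug.

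This mechanism works in one direction. A missed rescue can turn a failure into a responder, never the reverse. It raises CR, lowers rescue use and lengthens time to failure, and a larger sample does not remove it. The patients affected had nausea severe enough to bring them to emergency or inpatient care, so they are failures that the study would want to count.

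**Working it through.** **Step 1. Trace what each record can do to CR under the stated rule.**

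| Event in 0-120 h | Where recorded | Fails CR under Section 2.2? |
|---|---|---|
| Retching or vomiting | Retching/vomiting log; daily vomiting item | Yes |
| Antiemetic entered by the patient, any route | Rescue log | Yes |
| Yes on the rescue-log question, no row completed | Rescue log | Not stated |
| Staff-given antiemetic for nausea, not logged, entered in CRF | Concomitant-medication CRF | No stated route |
| ED visit or overnight stay ticked for nausea, nothing else logged | ED/hospital page | No stated route |

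The gap is in the last two rows. A visit for vomiting falls into it only if the emesis is also missing from the daily item and the log.

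**Step 2. Effect per patient.** The plan states no CR target or precision to reproduce. N is up to 200 with no formal calculation (Section 7.2). With m true failures counted as responders, CR is overstated by 100 × m / N points:

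- m = 1: 100 × 1/200 = 0.5 points
- m = 5: 100 × 5/200 = 2.5 points
- m = 10: 100 × 10/200 = 5.0 points

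Because 200 is a ceiling, each patient weighs more if fewer are evaluable in a cycle.

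**Step 3. Illustrative totals.** The documents give no rate of ED or hospital antiemetic treatment and no logging rate. Let v be the share of patients per cycle given such treatment without logged emesis, and u the share of those who leave the drug unlogged. Overstatement = 100 × v × u points. Both inputs are assumptions.

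| v | u = 25% | u = 50% | u = 100% |
|---|---|---|---|
| 1% | 0.25 | 0.5 | 1.0 |
| 3% | 0.75 | 1.5 | 3.0 |
| 5% | 1.25 | 2.5 | 5.0 |
| 10% | 2.5 | 5.0 | 10.0 |

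At N = 200 this is 0.5 to 20 patients. The range is wide because nothing in the documents narrows it.

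**Step 4. Scale against sampling error.** The 95% half-width is 1.96 × √(p(1 − p)/N). I use two overall CR figures from Section 1.4 for illustration:

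- p = 0.743: 1.96 × √(0.743 × 0.257/200) = 6.1 points
- p = 0.896: 1.96 × √(0.896 × 0.104/200) = 4.2 points

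It would take 13 or 9 misclassified patients respectively to move CR by that much (0.0606 × 200 = 12.1; 0.0423 × 200 = 8.5; both rounded up).

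**Step 5. If a contradictory diary is dropped.** Section 7.3 removes implausible or unclear data before analysis. If that removed one true failure from the denominator, CR would rise by p/(N − 1): 0.743/199 = 0.37 points, or 0.896/199 = 0.45 points. Exclusion would therefore bias CR in the same direction, slightly less than misclassification.

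**The case against.** The case against is substantial, and most of it stands.

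- **Staff-given drugs are not excluded.** A reader might infer from the word take that the log covers self-medication only. The intravenous example and the request for every administration contradict that.
- **Drug details are not needed.** A patient who cannot name the drug or dose can still tick Yes, and CR needs only the fact of rescue.
- **Vomiting is largely covered.** A reader might infer that patients treated in an ED for vomiting become responders. They would have to leave both the daily vomiting items and the retching/vomiting log negative or blank while ticking vomiting on the ED page.
- **Staff see the diary.** Study personnel review it with the patient, and concomitant medication is assessed at each visit from Visit 2. But no instruction tells them to check ED or hospital treatment against the log, so this lessens the gap without closing it.
- **Details are deferred.** Section 7.3 promises a full SAP before database lock, which could add the rule. No such rule is in the documents, and Section 2.2 already states a diary-only source.
- **Exclusion as unclear data is only a possibility.** Section 7.3 does not define the term or say that a whole diary would go.
- **An ED visit for nausea is not itself a failure.** CR is defined by emesis and rescue. Counting every nausea-ticked visit as failure would change the endpoint and could bias it downward. Resolving such cases from ED or ward charts would need data that Table 1 does not schedule.

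**Conclusion.** The point holds in a narrow form. The stated derivation uses the diary only, and neither the concomitant-medication CRF nor the ED/hospital page is reconciled with it. The exposed patients are mainly those given an antiemetic by ED or hospital staff for nausea alone who neither tick Yes nor log it. Each overstates that cycle's CR by 0.5 points at N = 200. The total is unknown, and the ranges above rest wholly on assumed rates.

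It is tempting to set this beside the 7.7-point difference (74.3 − 66.6) between the netupitant/palonosetron and palonosetron arms in Section 1.4. That is a between-arm contrast from a randomised trial and does not suit a descriptive endpoint with no comparator. A handful of cases would stay within sampling error, though unlike sampling error they all push the same way.

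CR, rescue use and time to failure are secondary. The primary endpoint, FLIE total score in cycle 1, is unaffected. This is a cheap improvement to the derivation and does not threaten the study's main result.

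**What to change.** 1. **Define rescue use in Sections 2.2, 6.7 and 7.3.** Rescue in 0-120 h is any of: a Yes on the rescue-log question; a rescue-log row; or a concomitant-medication CRF entry for an antiemetic given to treat, not prevent, nausea or vomiting. Use the earliest recorded time for time to failure and phase. The treat/prevent distinction matters because Section 5.1 includes scheduled dexamethasone after Day 1 for some regimens, and counting prophylaxis would err the other way. The CRF page is not reproduced in the documents, so confirm that it records indication and time of administration.
2. **Reword the rescue log** to ask about medication the patient *took or was given, including in an emergency department or hospital*.
3. **Query contradictions.** Where the ED/hospital page has nausea or vomiting ticked but no emesis or rescue is recorded, have the site query it at the existing diary review. Do not exclude the record as unclear, and do not count it as failure by default.
4. **Report the effect.** Give a sensitivity analysis that treats unresolved cases as failures, and state how many failures came only from the added source.

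The cost is protocol, SAP and diary wording, a cross-check against a CRF that sites already complete, and a few more queries. CR may come out slightly lower. Patient management does not change.
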